### **8.2.5.2 Statistical Methods for Safety Analyses**

Safety and tolerability will be assessed by clinical review of all relevant parameters including adverse experiences (AEs), laboratory tests, and vital signs. Summary statistics (counts, percentage, mean, standard deviation, etc.) will be provided for the safety endpoints as appropriate. The 95% confidence interval for the incidence rate of Grade 2 or higher adverse events with an immune etiology and the incidence rate of Grade 3-5 AEs will be provided.

### **8.2.5.3 Statistical Methods for Biomarker Analyses**

The evaluation of a general positive association between CPS and ORR will be investigated via standard logistic regression as well as generalized additive models. The potential to achieve a cut-off greater than CPS = 1% for defining a PD-L1 strongly positive population will involve a review of how the positive predictive value (PPV, response rate in those above a cut-off), negative predictive value (NPV, non-response rate in those below the cut-off), and fraction of patients defined as strongly positive change as a function of increasing cut-offs and whether there is evidence for a relative improvement in clinical utility relative to the 1% CPS cut-off. A PD-L1 strongly positive cut-off that maintains high NPV (e.g. near or above 90%) while achieving meaningful enrichment of response and largely capturing patients showing durable clinical benefit is sought. The profiles of PPV, NPV, and the percentage of patients above a given cut-off along with intervals quantifying the uncertainty in those profiles will be estimated as a function of potential cut-offs. Receiver operating characteristic curve analysis will also be used to understand the sensitivity and specificity profile and examine cut-offs that might be suggested based on the ROC curve and their appropriateness with regard to PPV and NPV. CPS ranges for any promising cut-offs will also have to be gauged in the context of practical implementation and interpretation by pathologists in clinical practice.

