### **3.2 Secondary Objective(s) & Hypothesis(es)**

In subjects with advanced/unresectable or metastatic urothelial cancer who are ineligible to receive cisplatin-based therapy:

1. Objective: To evaluate the anti-tumor activity of pembrolizumab (MK-3475) as 1L therapy in PD-L1 strongly positive, PD-L1 positive and all subjects
  - By duration of response (DOR) based on RECIST 1.1 by independent radiology review.
  - By progression-free survival (PFS) based on RECIST 1.1 by independent radiology review and overall survival (OS).
  - By PFS rate based on RECICST 1.1 by independent radiology review and OS rate at 6 and 12 months.
2. Objective: To establish a cut-point for PD-L1 strongly positive status if this is not determined by other biomarker discovery populations, investigate the association between PD-L1 protein expression by IHC and anti-tumor activity.
3. Objective: To determine the safety and tolerability of pembrolizumab (MK-3475) as 1L therapy.

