#### **8.2.4.3 Biomarker Discovery Population**

The biomarker analysis will be based on all subjects within the first 100 enrolled by time that are deemed clinically evaluable, which is defined as any subjects who received at least one dose of study drug and had week 9 and week 15 scans, or discontinued due to radiographic/clinical progression or death before reaching week 15. The biomarker discovery population will be identified through routine review of accumulating data.

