#### **8.2.5.1 Statistical Methods for Efficacy Analyses**

Efficacy will be available for PD-L1 strongly positive subjects, PD-L1 positive subjects, and all subjects. The first 100 study subjects (biomarker discovery population) will be evaluated for biomarker cut-point determination. The biomarker discovery population will be excluded from the primary and secondary objectives for the PD-L1 strongly positive subjects.

For the primary efficacy endpoint, the ORR based on RECIST 1.1 by independent radiology review, the point estimate, and 95% confidence interval (as determined by the upper and lower 97.5% one-sided confidence bounds) will be provided using an exact binomial distribution (Clopper and Pearson method). Subjects without response data will be counted as non-responders.

Duration of responses (DOR) based on RECIST 1.1 by independent radiology review will be summarized descriptively using Kaplan-Meier medians and quartiles. Only the subset of subjects who show a complete response or partial response will be included in this analysis. For PFS and OS, Kaplan-Meier (KM) curves, median estimates, and survival rates at 6 and 12 months based on the KM curves (95% CI is based on Greenwood's formula) will be

provided. Subjects without efficacy evaluation data or without survival data will be censored at Day 1.

A summary of the primary analysis strategy for the primary and secondary efficacy endpoints is provided in [Table 8](#).

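### The strongly positive cut-point is chosen partly for a high NPV in the discovery set, but no independent or optimism-corrected NPV is planned

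*Combined protocol and SAP*

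**What the plan says.** Section 8.2.5.3 reviews the positive predictive value (PPV, response rate above a cut-off), the NPV (non-response rate below it), the fraction above the cut-off and ROC curves as the cut-off rises. It seeks "A PD-L1 strongly positive cut-off that maintains high NPV (e.g. near or above 90%) while achieving meaningful enrichment of response". Intervals are planned around the PPV and NPV profiles.

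The data for this are set in 8.2.4.3: "The biomarker analysis will be based on all subjects within the first 100 enrolled by time that are deemed clinically evaluable". Section 8.2.9 lets more subjects be added to that set if needed.

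For the final analysis, 8.2.5.1 states: "Efficacy will be available for PD-L1 strongly positive subjects, PD-L1 positive subjects, and all subjects". Table 8 and the subgroup analyses in 8.2.8 use the same three groups. Section 8.2.4.1 removes the discovery subjects from the strongly positive analysis and keeps them in the other two.

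Secondary objective 2 in 3.2 is to set the strongly positive cut-point if other discovery populations have not done so, and to "investigate the association between PD-L1 protein expression by IHC and anti-tumor activity".

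**The concern.** The plan accepts that choosing a cut-point and estimating efficacy in the same subjects is unsafe, which is why discovery subjects are left out of the strongly positive analysis. That protection covers only one of the two quantities used to justify the cut-point. The confirmation-group ORR in strongly positive subjects is an independent PPV. Nothing planned gives the matching response rate below the cut-point in independent subjects.

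A cut-point that separates responders from non-responders needs support on both sides. If the only NPV on record is the one that helped to select the cut-point, the response rate below it will tend to look lower than it is, and the strongly positive label will look more useful than it is. The planned intervals show sampling error. They do not remove the bias from selection.

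**Working it through.** **The plan's own figures (8.2.7).** With 350 − 100 = 250 confirmation subjects and prevalence 1/3, the exact binomial gives P(X ≥ 75) = 88.3% and P(X ≥ 60) = 99.95%. These match the stated 88% and 99.9%. With exactly 0.33 the first is 85.9%, so the stated 33% acts as a rounded one third. The documents give no operating figure for the NPV.

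**What the final results can yield.**
- *At or above the cut-point, confirmation subjects:* reported directly (Table 8).
- *CPS <1%, all subjects:* obtainable by subtracting PD-L1 positive from all subjects, if every subject has a CPS, since both groups include the discovery set.
- *Below the cut-point, confirmation subjects:* not obtainable from Table 8, because the all-subject ORR includes the discovery set and the strongly positive ORR excludes it.

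**Precision (Clopper-Pearson, the method in 8.2.5.1), at an NPV of about 90%.**
- Discovery set: 100 × 2/3 ≈ 67 below the cut-point. 60/67 = 89.6%, 95% CI 79.7 to 95.7%, before any selection bias.
- Confirmation group: 250 × 2/3 ≈ 167 below. 150/167 = 89.8%, 95% CI 84.2 to 94.0%.
- If all 250 had CPS of at least 1%: prevalence of CPS ≥1% is 225/350 = 64.3%, so 0.33/0.643 = 51.3% would be strongly positive and 250 × 0.487 ≈ 122 below. 110/122 = 90.2%, 95% CI 83.4 to 94.8%, covering only CPS from 1% to the cut-point.

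**Chance at a single fixed cut-off.** With 67 below, an observed NPV of at least 90% needs 61 non-responders. P(X ≥ 61) is 10.7% if the true NPV is 85% and 25.2% if it is 87.5%.

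**Selection optimism (all assumed).** 100 evaluable subjects; CPS percentile uniform on 0 to 1; logistic response model with overall ORR 24.5%; candidate cut-offs every 5 points from the 40th to the 80th percentile; take the highest with apparent NPV of at least 90%; 20,000 simulated trials per slope. Apparent and true NPV are averaged over the trials that find a cut-off.

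| Slope (log-odds per unit percentile) | Trials finding a cut-off | Apparent NPV | True NPV | Optimism (points) |
|---|---|---|---|---|
| 1.5 | 16% | 91.1% | 82.1% | 9.0 |
| 2 | 27% | 91.1% | 84.0% | 7.2 |
| 3 | 57% | 91.2% | 87.0% | 4.2 |
| 4 | 82% | 91.3% | 88.9% | 2.4 |

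Optimism is taken from unrounded values. With cut-offs every 10 points, the slope 1.5 case finds one in 15% of trials, with similar optimism (9.1 points).

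Under a rule that ignores the 90% target and maximises the Youden index (ORR 20 to 30%, slopes 2 and 4, 10 candidate cut-offs above CPS 1%), the optimism is 2.1 to 2.8 points. The direction was upward in every scenario.

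**The case against.** The strongest reply is that NPV is neither an endpoint nor a listed objective, that 90% is only an example, and that the choice also weighs other things, such as "while achieving meaningful enrichment of response and largely capturing patients showing durable clinical benefit is sought", the ROC curve and practicality for pathologists. A rule that takes the highest passing cut-off is harsher on NPV than the text requires. Intervals are planned: 61/67 (91.0%) has an exact CI of 81.5 to 96.6%, which contains most of the true values in the table. If no useful cut-off is found, 8.1 and the note in 3.3 drop the strongly positive objectives, so no NPV would stand. If the cut-point came from other data, as 3.2 allows, this trial's NPV would not have been selected here. All of this stands. It limits the size of the problem but does not supply the missing estimate.

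Four stronger readings are tempting, and the documents do not support them.
- *Discovery is capped at 100 and confirmation fixed at 250.* Section 8.2.9 allows a larger discovery set, so both are planned figures.
- *No final estimate exists for CPS <1%.* It follows by subtraction for the whole trial, and 8.2.9 plans an interim one. Missing are the CPS 1%-to-cut group and any split limited to confirmation subjects.
- *The association objective uses only 100 of 350 subjects and so loses precision.* Section 8.2.4.3 makes the narrow population plausible, but 3.2 and the opening of 8.2.5.3 name none. It is unspecified rather than restricted.
- *The NPV will be about 9 points too high.* That applies to a weak association, where most trials would find no qualifying cut-off.

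**Conclusion.** The gap is real and moderate. The cut-point is chosen partly on its NPV in the discovery set, the confirmation subjects re-estimate only the response rate above it, and no independent or bias-corrected NPV is planned. The discovery NPV should be expected to err upward. Where a qualifying cut-off is found in most runs (slopes 3 and 4), the assumed rule gives about 2 to 4 points. The larger figure of about 7 to 9 points is conditional on an outcome seen in about 15 to 27% of runs. These sizes depend on a selection rule and an association strength that the documents do not give.

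A reader might infer that the primary results are biased. They are not: discovery subjects are excluded from the strongly positive ORR, and the all-subject and PD-L1 positive groups do not depend on this cut-point. What lacks independent support is a claim that the cut-point separates responders from non-responders.

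**What to change.** Amend 8.2.5.3 and Table 8 as follows.

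1. At the locked cut-point, report in the non-discovery subjects the ORR with exact 95% CI above and below it, and the difference. Show CPS <1% and CPS 1%-to-cut separately. If enrolment of CPS <1% was stopped under 8.2.9, state that the below-cut estimate covers only CPS 1%-to-cut (about 122 rather than about 167 of 250, if the stop applied to the whole confirmation group). Label the discovery NPV as apparent.
2. State that the logistic and generalized additive models for secondary objective 2 are run at the final analysis in all treated subjects with a CPS, not only in the discovery set.
3. If the three ORRs are presented together, also give the all-subject and PD-L1 positive ORRs in the non-discovery subjects, so that the comparison rests on one set of subjects.

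The cost is some SAP wording and a few tables from data already collected. The drawback for the sponsor is that the held-out NPV may be lower than the discovery figure.

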**Table 8 Analysis Strategy for Efficacy Endpoints**

Endpoint/Variable ‡ (Description, Time Point)	Statistical Method	Analysis Population	Missing Data Approach
Primary Objectives:			
RECIST1.1 ORR by independent radiology review for PD-L1 strongly positive subjects, PD-L1 positive subjects, and all subjects	Exact method based on binomial distribution	APT/FAS	Subjects with missing data are considered non-responders
Secondary Objectives:			
Duration of Response, RECIST1.1 by independent radiology review, for PD-L1 strongly positive subjects, PD-L1 positive subjects, and all subjects	Summary statistics /Kaplan-Meier method	APT/FAS	Non-responders are excluded in analysis
Progression-free survival, RECIST1.1 by independent radiology review, for PD-L1 strongly positive subjects, PD-L1 positive subjects, and all subjects	Summary statistics /Kaplan-Meier method	APT/FAS	Censored at last assessment
Overall survival, for PD-L1 strongly positive subjects, PD-L1 positive subjects, and all subjects	Summary statistics /Kaplan-Meier method	APT/FAS	Censored at last assessment
95% confidence interval is determined by the upper and lower 97.5% one-sided confidence bounds.			

### 8.2.5.4 Summaries of Baseline Characteristics, Demographics, and Other Analyses

#### 8.2.5.4.1 Demographic and Baseline Characteristics

Baseline characteristics will be assessed by the use of tables and/or graphs for each cohort. No statistical hypothesis tests will be performed on these characteristics. The number and percentage of subjects screened, randomized, primary reasons for screening failure, and discontinuation will be displayed. Demographic variables (e.g., age, gender), baseline characteristics, primary and secondary diagnoses, and prior and concomitant therapies will be summarized by treatment either by descriptive statistics or categorical tables.

#### 8.2.6 Multiplicity

This is an estimation study. 95% confidence intervals of ORR will be provided. No multiplicity adjustment will be applied.

#### 8.2.7 Sample Size and Power Calculation

The sample size is driven by the primary efficacy estimation for PD-L1 strongly positive subjects. [Table 9](#) and [Table 10](#) shows 95% CIs at different true ORR rates (number of events), for 60 and 75 PD-L1 strongly positive subjects, respectively.

**Table 9** Estimates and 95% CIs with 60 PD-L1 Strongly Positive Subjects

Sample Size	Number of ORR Event	Proportion	Lower Limit	Upper Limit	Width of 95% CI
60	12	0.2	0.108	0.323	0.215
60	13	0.217	0.121	0.342	0.221
60	14	0.233	0.134	0.36	0.227
60	15	0.25	0.147	0.379	0.231
60	16	0.267	0.161	0.397	0.236
60	17	0.283	0.174	0.414	0.24
60	18	0.3	0.188	0.432	0.244
60	19	0.317	0.203	0.45	0.247
60	20	0.333	0.217	0.467	0.25
60	21	0.35	0.231	0.484	0.253
60	22	0.367	0.246	0.501	0.255

**Table 10** Estimates and 95% CIs with 75 PD-L1 Strongly Positive Subjects

Sample Size	Number of ORR Event	Proportion	Lower Limit	Upper Limit	Width of 95% CI
75	20	0.267	0.171	0.381	0.21
75	21	0.280	0.182	0.396	0.214
75	22	0.293	0.194	0.41	0.216
75	23	0.307	0.205	0.424	0.219
75	24	0.320	0.217	0.438	0.221
75	25	0.333	0.229	0.452	0.223
75	26	0.347	0.24	0.465	0.225
75	27	0.360	0.252	0.479	0.227
75	28	0.373	0.264	0.493	0.229
75	29	0.387	0.276	0.506	0.23
75	30	0.400	0.288	0.52	0.232

Up to 350 subjects will be enrolled. Assuming a 33% prevalence rate of PD-L1 strongly positive subjects and 100 for biomarker discovery population, there is 88% chance to have at least 75 PD-L1 strongly positive subjects and 99.9% chance to have at least 60 PD-L1 strongly positive subjects in the confirmation group.

For all and PD-L1 positive subjects, the expected sample sizes (350 and 225, respectively) are adequate for efficacy estimation. Thus, if strongly PD-L1 positive cannot be determined, the study may stop enrollment after ~225 subjects are enrolled.

### **8.2.8 Subgroup Analyses and Effect of Baseline Factors**

To determine whether the treatment effect is consistent across various subgroups, the estimate (with a nominal 95% CI) for the primary endpoint will be estimated and plotted within each category of the following classification variables for all subjects, PD-L1 positive subjects, and PD-L1 strongly positive subjects, respectively:

- Age category ( $\leq 65$  vs.  $> 65$  years)
- Sex (female vs. male)
- Race (white vs. non-white)
- ECOG status (0 / 1 vs. 2 and 0 vs 1 / 2)
- Geographic region of enrolling site (East Asia vs. non-East Asia and EU vs. non-EU)
- Presence or absence of liver metastases at baseline
- Baseline hemoglobin ( $\geq 10$  g/dL vs.  $< 10$  g/dL)
- Naïve vs. prior adjuvant/neoadjuvant chemotherapy
- Bajorin risk score

The consistency of the treatment effect will be assessed descriptively via summary statistics by category for the classification variables listed above.

### **8.2.9 Interim Analyses**

A biomarker analysis is planned where data from a subset of subjects (the biomarker discovery population) will be used to determine the PD-L1 strongly positive cut-point. The biomarker discovery population consists of the evaluable subjects among the first 100 subjects enrolled into the study. Analysis will be conducted according to the SAP (section 8.2.5.3). More subjects may be allocated to the biomarker discovery population, if necessary.

In addition, an interim efficacy evaluation for the PD-L1 negative population will be performed using the biomarker discovery population data. Enrollment of PD-L1 negative (CPS  $< 1\%$ ) population may be stopped if the ORR is low and substantial enrollment remains. The futility analysis will be based on the evaluable PD-L1 negative subjects in the biomarker discovery population (up to the first 25 subjects). If the number of PD-L1 negative subjects in the biomarker subgroup is less than 20, additional PD-L1 negative subjects may be included until the number reaches at least 20. The non-binding rule for futility is the upper limit of the 95% CI (two-sided) of the ORR estimate is less than 20% (need at least 1 response in  $N < 26$  subjects, and at least 2 responses in  $N = 26$  to 40 subjects).

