The primary objective of this study is to evaluate the anti-tumor activity of pembrolizumab (MK-3475) as firstline (1L) therapy in subjects with advanced/unresectable (inoperable) or metastatic urothelial cancer who are ineligible for cisplatin-based therapy and whose tumors express PD-L1 protein by IHC based on ORR (RECIST 1.1) assessed by independent radiology review. Data from previously conducted pembrolizumab bladder cancer trials will be utilized to determine a biomarker assay cut-point. In the event a cut-point cannot be determined from data from previous studies, additional subjects will be added to the beginning of this study to supplement the previously collected data in order to determine the assay cut-point. In this case, data from subjects in the main part of the trial to assess the primary endpoint will be kept separate, and will be analyzed separately once the cut-point has been determined.

The all-patient-treated (APT) population will serve as the primary population for the analyses of efficacy data in this trial. Supportive analyses of efficacy will be conducted in the full analysis set (FAS) population as well. The APT population consists of all treated subjects. The FAS population consists of all enrolled subjects who receive at least one dose of study treatment and have measurable disease at baseline. Interim futility analysis with PD-L1 negative subjects is planned and enrollment of PD-L1 negative subjects may be stopped after the interim analysis.

Participation in this trial will be dependent upon supplying tumor tissue obtained at any time before the first dose of study drug, as long as the subject has not received any intervening systemic therapy from the time the tissue was collected until the time the subject enters the study.

Additionally, tumor tissue must be obtained from locations not radiated prior to biopsy; newly obtained formalin-fixed specimens AFTER the subject has been diagnosed with metastatic or muscle invasive disease will be required for determination of PD-L1 status. Biopsies obtained PRIOR to receipt of neoadjuvant/adjuvant chemotherapy are NOT permitted. Subjects who received neoadjuvant/adjuvant therapy are permitted onto the trial as long as therapy was completed at least 12 months prior to the diagnosis of metastatic disease.

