### 3.0 OBJECTIVE(S) & HYPOTHESIS(ES)

#### 3.1 Primary Objective(s) & Hypothesis(es)

In subject with advanced/unresectable or metastatic urothelial cancer who are ineligible to receive cisplatin-based therapy, evaluate anti-tumor activity of pembrolizumab (MK-3475) as 1L therapy:

1. Objective: By objective response rate (ORR) based on RECIST 1.1 by independent radiology review in all subjects.
2. Objective: By ORR based on RECIST 1.1 by independent radiology review in subjects whose tumors are PD-L1 positive (Combined Positive Score or CPS  $\geq$  1%).
3. Objective: By ORR based on RECIST 1.1 by independent radiology review in subjects whose tumors are PD-L1 strongly positive (CPS cut-point determined from biomarker discovery population; see Section 8.2).

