## **8.2.4 Analysis Populations**

### **8.2.4.1 Efficacy Analysis Population**

The APT population, which consists of all enrolled subjects who receive at least one dose of study treatment, will serve as the primary population for the analyses of efficacy data in this trial. Supportive analyses of efficacy will be conducted in the full analysis set (FAS) population, which consists of all enrolled subjects who receive at least one dose of study treatment and have measurable disease at baseline.

The biomarker discovery population, subjects in this trial used for the determination of the PD-L1 strongly positive cut-point, will be excluded from efficacy analyses for the PD-L1 strongly positive population. These subjects will still be included in the efficacy analyses for all and PD-L1 positive subjects.

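### If CPS<1% enrolment alone is stopped under 8.2.9, the pooled all-subjects ORR becomes PD-L1-enriched, and the plan neither labels it nor gives an all-comer figure

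*Combined protocol and SAP*

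**What the plan says.** Section 3.1 lists as the first primary objective, in cisplatin-ineligible patients, to evaluate activity "By objective response rate (ORR) based on RECIST 1.1 by independent radiology review in all subjects". Section 2.1 states that "enrollment of PD-L1 negative subjects may be stopped after the interim analysis". Section 8.2.9 repeats the option: the CPS<1% "population may be stopped if the ORR is low and substantial enrollment remains". The rule is non-binding. It is met when the upper 95% limit for the ORR in negatives is below 20%, judged on up to 25 evaluable negatives from the discovery group. It has a floor: "If the number of PD-L1 negative subjects in the biomarker subgroup is less than 20, additional PD-L1 negative subjects may be included" until there are at least 20.

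The analysis does not change if the option is used. Of the discovery subjects, Section 8.2.4.1 says "These subjects will still be included in the efficacy analyses for all and PD-L1 positive subjects". Under Section 8.2.5.1 the point estimate and interval "will be provided using an exact binomial distribution (Clopper and Pearson method"). Table 8 has a single row for "RECIST1.1 ORR by independent radiology review for PD-L1 strongly positive subjects, PD-L1 positive subjects, and all subjects", with the exact binomial method. No section weights, restricts or relabels the all-subjects ORR, PFS or OS after a negatives-only stop, and CPS<1% versus ≥1% is not in the subgroup list in 8.2.8.

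**The concern.** Before a stop, subjects enter whatever their PD-L1 status, so the pooled ORR estimates the rate in the all-comer mix. After a stop, new subjects are all CPS≥1%, and the pooled mix is set by the trial's own adaptation and by when it was made.

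The rule also tends to act where this matters most, because it is met mainly when negatives rarely respond. The first primary estimate could then be read as an all-comer rate, and set against the 30% reference in Section 4.2.3.1.1, when it is closer to the rate in positives. This is an estimation-only trial, so the estimate and its interval are the result.

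**Working it through.** **Plan's own figures.** Clopper-Pearson upper limits are 16.8% for 0/20, 13.7% for 0/25, 20.4% for 1/25 and 19.6% for 1/26. This reproduces the bracket in 8.2.9 for fewer than 26 negatives: with 20 to 25, the rule is met only with zero responses. The 88% chance in 8.2.7 of at least 75 strongly positive subjects also reproduces, with 250 confirmation subjects at a prevalence of 1/3 (0.883). That calculation assumes an unenriched mix.

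**How often the rule is met** (25 negatives):
- negative ORR 2%: 0.98^25 = 0.60
- negative ORR 5%: 0.95^25 = 0.28
- negative ORR 10%: 0.90^25 = 0.07

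**Inputs.**
- N = 350 (8.2.7).
- Natural negative share q: not stated. The expected 225 positives of 350 in 8.2.7 imply q = 125/350 = 0.357. A share of 0.25 is taken as an alternative.
- ORR in positives p₊ = 30%. This is an assumption, borrowed from the reference rate in 4.2.3.1.1.
- ORR in negatives p₋ = 5%. This is an assumption.
- S, the number enrolled when the stop takes effect: assumed 150, 200 or 250. Evaluable subjects must have "received at least one dose of study drug and had week 9 and week 15 scans", or have stopped earlier for progression or death, so accrual runs on while scans mature. No accrual rate is given.
- m ≈ 25 interim negatives, with zero responses if the rule was met.

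**Formulas.** The target is T = (1−q)p₊ + q·p₋. The pooled negative share after a stop is qS/N, if later places go to positives. Given a stop,

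expected crude ORR − T = q(1 − S/N)(p₊ − p₋) − m·p₋/N.

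The first term is enrichment. The second is the small offset from conditioning on zero interim responses.

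**Stop at 150, q = 0.357.** T = 0.643×0.30 + 0.357×0.05 = 21.1%. The pooled negative share is 0.357×150/350 = 15% instead of 36%. The difference is 0.357×0.571×0.25 − 25×0.05/350 = 0.0510 − 0.0036 = +4.7 points.

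**Stop at 150, q = 0.25.** The pooled negative share is 11% instead of 25%. The difference is 0.25×0.571×0.25 − 0.0036 = +3.2 points.

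Simulation under the same set-up (random CPS mix, top-up to 20 negatives) gives the same differences and the coverage of T by the 95% interval:

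| Negative share | Stop at 150 | Stop at 200 | Stop at 250 |
|---|---|---|---|
| 36% | +4.7 (46%) | +3.5 (68%) | +2.2 (85%) |
| 25% | +3.2 (73%) | +2.3 (84%) | +1.4 (91%) |

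**Sensitivity.**
- Vacated places left unfilled, 30%/5%: +3.7, +2.5, +1.4 at a 36% share; +2.7, +1.9, +1.1 at 25%.
- 30%/10%, 25% share: +2.2, +1.5, +0.7 (87, 92, 95%).
- 30%/15%, 25% share: +1.2, +0.6, +0.1 (93, 95, 96%).
- Equal ORRs: the first term vanishes and the crude rate is slightly low. At 10%, −25×0.10/350 = −0.7 points; at 15%, −1.1.
- Over all trials, stopped or not, with every met rule acted on, 30%/5%: coverage 82, 88, 93% at a 36% share and 89, 92, 94% at 25%.

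**The case against.** The strongest reply is that the plan defines its primary population as all treated subjects, and the crude proportion describes that set correctly. No section says that objective 1 targets the ORR at natural PD-L1 prevalence, so bias and coverage exist only against a target that a reader supplies. This stands in part. But Section 3.1 names the cisplatin-ineligible population, and all-subjects and CPS≥1% results are separate objectives. An all-comer reading of the first is the natural one, and nothing in the plan warns against it after a stop.

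Other points that stand:
- ORR is planned for both all and CPS≥1% subjects, so negatives can be recovered by subtraction, apart from any without a CPS result. The enrichment would be visible. A pre-stop estimate would not be recoverable.
- There is no hypothesis test, so no error rate is affected. The sample size is driven by strongly positive subjects.
- PD-L1 is evaluated retrospectively (7.1.2.7), the study team is blinded to scores (8.2.1), and no eligibility criterion excludes CPS<1%. A stop would probably need an amendment, which could address the analysis. Sections 2.1 and 8.2.9 nevertheless authorise the stop now.
- The lowest coverage figures are conditional on a stop and need an early stop, a high negative share and a wide ORR gap.

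A reader might also infer from the clause on fewer than 20 negatives that the sponsor expects a negative share well below 36%. The documents do not support this, because the clause counts only evaluable subjects. At a 36% share, the chance of fewer than 20 negatives is 0.02% with 100 evaluable, but 1.5% with 80 and 8% with 70. The evaluable fraction is not stated.

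**Conclusion.** The point holds in conditional form. If CPS<1% enrolment is stopped, CPS≥1% enrolment continues and negatives respond clearly less often, the pooled all-subjects ORR overstates the rate in the mix enrolled before the stop. At 30% versus 5%, for stops between 150 and 250, the excess is about 2 to 5 points at a 36% negative share and about 1 to 3 points at 25%. It shrinks with a later stop or a narrower gap, and turns slightly negative if the ORRs are equal. The direction under a clear gap is firm. The size is not, because negative share, ORR by PD-L1 status and timing of the stop are all assumed.

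A reader might go further and conclude that the all-subjects ORR is biased as planned, or that the PD-L1 results are compromised. Neither follows. Without a stop the pooled rate is sound, the rule is non-binding and met only about 28% of the time at a negative ORR of 5% (7% at 10%), and the CPS≥1% and strongly positive estimates do not depend on how many negatives are enrolled. No size has been computed for PFS or OS. This is a cheap improvement.

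**What to change.** Add to Section 8.2.5.1 and Table 8:

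> If enrolment of CPS<1% subjects is stopped, the crude pooled all-subjects ORR is still reported but is labelled PD-L1-enriched and is not interpreted as the all-comer ORR. The all-comer ORR is reported from subjects enrolled before the stop (Clopper-Pearson 95% CI), together with the ORR in each CPS stratum. The report notes a small downward selection bias, because a stop requires few or no interim responses. All-subject PFS and OS carry the same label and are also shown for pre-stop subjects.

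The cost is SAP wording and a few table rows. The pre-stop interval is wider: half-width about 6.7 points against 4.7 for the crude rate, for a stop at 150 and a 36% share. Its downward bias is about m·p₋/S: at 30%/5%, 25×0.05/150 = 0.8 points for a stop at 150 and 25×0.05/250 = 0.5 for a stop at 250, with coverage of about 96% at a 36% share. With a very early stop and a negative ORR of 10% it reaches 25×0.10/100 = 2.5 points. If both ORRs are 10% and the stop is at 100, pre-stop coverage is 88% against 95% for the crude rate, so both should be shown.

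An estimate reweighted to the pre-stop CPS proportions is at most an optional sensitivity analysis. At a 36% share its coverage falls to 87% at 30%/10% with a stop at 150, and to 76% or 57% at 10%/10% with a stop at 150 or 100.
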